7.3. Vital Signs

Descriptive statistics for body weight and vital signs (ie, oral temperature, supine systolic and diastolic blood pressure, and pulse) and changes from baseline values at each time point will be presented by treatment group, and all the data will be listed. If there are multiple measurements for the same time point, the first one will be used for the by-time point analysis.

The number and percentage of subjects with PCS postbaseline vital signs will be tabulated by treatment group (or cohort). A vital sign value will be considered PCS if it meets both the observed value criterion and the change from baseline criterion. The criteria for PCS vital sign values are detailed in [Table 3](#). The PCS percentages will be calculated relative to the number of subjects with baseline values and at least 1 assessment in the postbaseline period. The numerator will be the total number of subjects with available baseline values and at least 1 postbaseline PCS value.

A supportive data listing for subjects with PCS postbaseline values will be provided, including the subject ID number, baseline and postbaseline values for each visit, and a flag indicating the PCS vital sign values.

Table 3: Criteria for Potentially Clinically Significant Vital Signs

Vital Sign Parameter	Flag	Criteria ^a	
		Observed Value	Change from Baseline
Supine systolic blood pressure (mmHg)	High	≥180	Increase of ≥20
	Low	≤90	Decrease of ≥20
Supine diastolic blood pressure (mmHg)	High	≥105	Increase of ≥15
	Low	≤50	Decrease of ≥15
Supine pulse (beats per minute)	High	≥120	Increase of ≥15
	Low	≤50	Decrease of ≥15
Weight (kg)	High	-	Increase of ≥7%
	Low	-	Decrease of ≥7%

^a A postbaseline value is considered as a PCS value if it meets the criteria for both observed value and change from baseline.

In addition to supine measurements, at the predose measurement and at various postdose time points on days 1, 2, 7 and 8, standing blood pressure and pulse will be measured 3 minutes after the supine measurements are taken. The change in blood pressure from supine to standing, along with associated adverse events, will be used to assess orthostatic hypotension. The criteria for testing positive for orthostatic hypotension are presented in [Table 4](#).

Table 4: Criteria Associated with Orthostatic Hypotension

Blood Pressure Parameter	Blood Pressure Change from Supine to Standing
Systolic blood pressure (mmHg)	Decrease of ≥20 mmHg
Diastolic blood pressure (mmHg)	Decrease of ≥10 mmHg

Subjects meeting either one of these two criteria and who also have an associated adverse event, as indicated on the eCRF, are considered to be positive for orthostatic hypotension. The number and percent of subjects who have an orthostatic hypotension event will be tabulated by treatment group (or cohort) and by period (baseline versus postbaseline).

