2.3.1. Risk Assessment

Potential Risk of Clinical Significance	Summary of Data/Rationale for Risk	Mitigation Strategy
Study Intervention: IW-3300		
Potential for diarrhea and secondary dehydration	These are class effects of GC-C agonism or effects observed in nonclinical safety pharmacology and toxicology studies of IW-3300.	Intrarectal administration will likely decrease the risk of diarrhea and subsequent dehydration. The study design includes dose escalation to closely monitor subject safety and tolerability at each dose level before dosing with a higher dose; a Dose Escalation Committee will conduct blinded reviews of all the safety parameters of the dosing cohort through Discharge (Day 8) in order to make decisions regarding escalation to the next dose. Orthostatic vital sign measurements will be taken to evaluate the potential for volume depletion. The daily bowel movement (BM) frequency and stool consistency will be monitored in real time to evaluate changes in bowel habits and the potential risk of diarrhea. Stopping rules will also be in place to evaluate continued dosing (Section 7.1.1); dosing within a cohort may be temporarily suspended in the event of a diarrhea or dehydration serious adverse event (SAE); ≥ 1 subject with Grade 3 diarrhea (increase from baseline of >7 stools per day and/or watery stools [Bristol Stool Form Scale {BSFS} score of 7] resulting in a limiting of self-care activities) or dehydration (hospitalization indicated); or ≥ 3 subjects with Grade 2 diarrhea (increase from baseline of 4 to 6 stools per day and/or watery stools [BSFS score of 7] resulting in a limiting of instrumental activities) or dehydration (intravenous fluids indicated).

Potential Risk of Clinical Significance	Summary of Data/Rationale for Risk	Mitigation Strategy

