9. STATISTICAL CONSIDERATIONS

9.1. Statistical Hypotheses

No hypothesis testing is planned.

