4.1.1. Number of Subjects

A total of up to 27 subjects will be randomized in the study (2 cohorts of 9 subjects each, and an optional 3rd cohort of 9 additional subjects). Within each cohort, 6 subjects will be randomized to IW-3300 and 3 subjects will be randomized to placebo.

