4.5. Sample Size and Power Considerations

No statistical sample size determination process was performed. The sample size chosen for each cohort (9 subjects) is considered sufficient for evaluation of safety, tolerability, PK, and microbiome.

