7. SAFETY ANALYSIS

All safety parameters will be summarized using descriptive statistics. Safety analyses will be performed on the Safety Analysis Set. The safety parameters will include AEs, clinical laboratory evaluations, vital signs, and ECGs. For each laboratory parameters and ECG site interpretation, the last nonmissing assessment before the first dose of study drug will be used as the baseline for all analyses of that laboratory parameter or ECG interpretation. For numeric ECG measurements, the average of the last triplicate ECG before dosing will be used as baseline. For vital signs, the last supine measurement before dosing will be used as baseline.

All safety analyses will be performed according to the treatment actually received regardless of the allocated treatment. All subjects on placebo arm will be pooled from available cohorts, whenever appropriate, to conduct analyses.

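### The supine-to-standing blood pressure change has no planned continuous summary; it is tabulated only as an event that also requires an associated adverse event, so a graded or symptom-free fall would appear only in listings

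*SAP*

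**What the plan says.** Protocol 2.3.1 names diarrhea with secondary dehydration as the first risk of the study drug and gives the reason for the measurement: "Orthostatic vital sign measurements will be taken to evaluate the potential for volume depletion". Protocol 8.2.2 and the Schedule of Activities place supine and standing pressure and pulse at Day 1 predose, 1 h and 6 h; Day 2 predose; Day 7 predose, 1 h and 6 h; and Day 8.

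SAP 7.3 plans "Descriptive statistics for body weight and vital signs (ie, oral temperature, supine systolic and diastolic blood pressure, and pulse"), with changes from baseline at each time point. SAP 7 sets the vital-sign baseline as the last supine value before dosing, and the Table 3 criteria for blood pressure and pulse are also supine.

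For the postural readings, SAP 7.3 says: "The change in blood pressure from supine to standing, along with associated adverse events, will be used to assess orthostatic hypotension". Table 4 sets the cut at a fall of at least 20 mmHg systolic or 10 mmHg diastolic. A subject is positive only if one of these is met and there is also an associated adverse event on the eCRF. The output is a number and percent of such subjects by treatment group (or cohort), split into baseline and postbaseline. SAP 7.3 also says that all the data will be listed.

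**The concern.** A continuous measurement, taken repeatedly for a named safety purpose, is reduced to one yes/no result per subject per period. Two steps lose information. The cut discards the size of the fall, and the adverse-event condition then discards falls that were measured but caused no recorded symptom. With 6 subjects per dose, a shift in the whole group's postural response could leave the table empty or nearly so.

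What is at stake is the final safety description, which the protocol synopsis says will be used to enable a Phase 2 study. If the drug produces a modest, mostly symptom-free postural fall that grows with dose, no planned table would show its size, timing or dose ordering.

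**Working it through.** **Consistency within the plan.** The SAP treats comparable safety measures differently:

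| Measure | Continuous summary | Threshold count |
|---|---|---|
| Laboratory values (7.2) | yes, with change from baseline | yes |
| Supine blood pressure and pulse (7.3) | yes, with change from baseline | yes |
| ECG intervals (7.4) | yes, with change from baseline | yes |
| Supine-to-standing blood pressure change (7.3) | none | yes, and only with an associated AE |

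Standing pulse is collected, but no analysis of it is specified.

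**Inputs from the documents.**
- Orthostatic time points: 3 + 1 + 3 + 1 = 8, of which 1 is baseline and 7 are postbaseline.
- Allocation (SAP 4.1.1): "Within each cohort, 6 subjects will be randomized to IW-3300 and 3 subjects will be randomized to placebo".
- Comparator (SAP 7): "All subjects on placebo arm will be pooled from available cohorts, whenever appropriate, to conduct analyses". This gives 6 placebo subjects with two cohorts and 9 with three.
- There is no figure of the plan's own to reproduce. SAP 4.5: "No statistical sample size determination process was performed". Protocol 9.1: "No hypothesis testing is planned". Power is used below only as a yardstick for information.

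**Assumptions, not in the documents.** Normal postural systolic change; placebo mean 0; SD 10 mmHg; correlation 0.5 between readings in one subject; a constant extra fall of 10 mmHg; systolic criterion only; where the AE condition is applied, 30% of subjects with a qualifying fall have an associated AE, in either arm.

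**Continuous summary (each subject's mean of seven readings).**
- Variance = 10² × (0.5 + 0.5/7) = 57.1, so SD = 7.56 mmHg.
- Standard error, 6 vs 6 = 7.56 × √(1/6 + 1/6) = 4.36. Effect / SE = 10/4.36 = 2.29.
- Two-sided 5% power, t-test with 10 degrees of freedom: about 54%.

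**Yes/no count.** By simulation, 47% of active subjects reach a 20 mmHg fall at one or more of the seven readings.
- Every fall counted: P(0/6) = (1 − 0.47)⁶ = 0.02.
- With the AE condition: 0.47 × 0.30 = 0.14 positive per subject, so P(0/6) = (1 − 0.14)⁶ = 0.40.
- Fisher's exact test, 6 vs 6: 4/6 against 0/6 gives p = 0.061 and 5/6 against 0/6 gives p = 0.015. A dose therefore needs 5 of 6 positive to separate from an empty placebo group.

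| SD 10, shift 10 mmHg | Subject mean | Every fall counted | Planned count, 30% AE rate |
|---|---|---|---|
| 6 vs 6 placebo | about 54% | about 5% | near 0% |
| 6 vs 9 placebo | about 64% | about 28% | about 3% |

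**Range.** A second simulation used placebo, 100 µg and 300 µg with 6 subjects each, SD 8 to 12, a 5 or 10 mmHg fall at 300 µg and one third of that at 100 µg.
- The planned table has no events in any group in 14–66% of trials at a 30% AE rate, and in 53–87% at a 10% AE rate.
- A linear dose slope on subject means is detected in 13–30% of trials for 5 mmHg and in 44–79% for 10 mmHg.
- Fisher's test of 300 µg against placebo is positive in at most 6.4% of trials if every fall counts, and in at most 0.1% at either AE rate.

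**Precision of the proposed mean.** For n = 6 at one time point, the 95% half-width is 2.571 × SD/√6: 8.4, 10.5 and 12.6 mmHg for SD 8, 10 and 12.

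**The case against.** Several stronger readings are tempting, and the documents do not support them.

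- **That a graded fall cannot be seen at all.** All the data are to be listed, so 6 subjects × 8 readings per dose can be inspected. That stands, although a listing gives no group comparison.
- **That dose escalation rests on this table.** It does not. Protocol 6.3.2 and 6.6 give that decision to a committee reviewing blinded safety and tolerability data through Day 8. A by-treatment table at study end could not inform it. Nor does any text tie the Phase 2 dose choice to this table.
- **That the cut alone would leave the dose group looking like placebo.** One reading might suggest so: 16% positive gives (1 − 0.159)⁶ = 0.36 for 0/6. But the planned count covers the whole postbaseline period. Over seven readings with every fall counted, about 2.8/6 active against 0.6/6 placebo would be expected, and 0/6 occurs in about 2% of trials. The AE condition is what makes the table sparse.

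Other points on that side have weight. Protocol 9.4.5 plans blood pressure summaries without limiting them to supine, but it does not name the postural change, and the more detailed SAP specifies supine. Dehydration is also followed through laboratory values, weight, bowel movements and adverse events. No test is planned, and every SD, shift and AE rate above is assumed. Counting diastolic falls, or a higher AE rate among larger falls, would help the count.

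The proposed mean has its own weakness. Under Protocol 8.2.2, subjects with symptoms on standing lie down without the 3-minute wait. If their standing values are missing, the mean would be biased toward no effect.

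**Conclusion.** The point holds as a gap in the planned displays. The measure the protocol chose for volume depletion has no continuous summary, and its only table requires both a threshold fall and an associated adverse event. Graded or symptom-free falls are left to listings.

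The size depends on assumptions. In the base case the yardstick falls from about 54% to about 5% through the cut, and to near 0% once a 30% AE rate is applied. With 9 placebo subjects it is about 64%, 28% and 3%. The direction does not depend on the particular SD or shift: the continuous summary was ahead in every setting run. It would still be imprecise with 6 subjects, but it would show direction, size and dose ordering.

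The consequence is confined to the end-of-study safety conclusions. The primary endpoints and the escalation process are not affected.

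**What to change.** In SAP 7.3, before database lock:

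1. Add descriptive statistics (n, mean, SD, median, minimum, maximum) by treatment group at each scheduled orthostatic time point for the supine-to-standing change in systolic pressure, diastolic pressure and pulse, and for its change from the Day 1 predose value.
2. At each time point, report how many subjects had no 3-minute standing reading because of symptoms, so that the means can be read with that in mind.
3. Beside the AE-conditional count, add a count of subjects meeting Table 4 regardless of adverse events, by the same periods.

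The cost is one or two extra tables from data already collected. There is no protocol change and no added procedure. The means will have wide intervals (about ±10.5 mmHg at SD 10) and should be presented as descriptive.

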Dosing in Cohort 2 and optional Cohort 3 will only proceed following a review of safety data from the previous cohort(s), including adverse events (AEs), clinical laboratory test results, vital signs, and 12-lead ECGs. The determination of dose escalation will be made at a meeting of the Dose Escalation Committee.

Treatment duration will be 7 days; subjects will be followed in the Phase 1 clinical research unit (CRU) for the duration of dosing, until at least 24 hours after the last dose of study drug and

[figure not shown]
contacted by phone for follow-up approximately 2 weeks after the last dose. Total subject participation will be 29 to 57 days, including the Screening, Clinic, and Follow-up Periods.

Data Monitoring Committee: No

The study will utilize a Dose Escalation Committee to review safety data for Cohort 1 in order to make decisions about dose escalation to Cohort 2. An optional cohort, Cohort 3, may be enrolled based on a review of safety data from Cohorts 1 and 2.

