8.2.2. Vital Signs

Vital signs will be performed as outlined in the SoA ([Table 1](#)).

- Vital signs will include oral temperature, blood pressure, and pulse rate.
- Blood pressure and pulse measurements will be assessed with a completely automated device. Manual techniques will be used only if an automated device is not available.
- In a semisupine position, blood pressure and pulse will be obtained at the 0.5-hour postdose timepoint on Days 1 and 7 (consistent with the position required following dosing).
- Blood pressure and pulse at the 2-, 4-, and 8-hour postdose timepoints on Days 1 and 7, as well as predose on Days 3 through 6, should be preceded by at least 5 minutes of rest for the subject in a quiet setting without distractions (eg, television, cell phones).
- At all other timepoints (ie, Day 1 predose and 1- and 6-hours postdose, Day 2 predose, Day 7 predose and 1- and 6-hours postdose, and Day 8 [24-hours post-Day 7 dose]), orthostatic blood pressure and pulse measurements will be obtained. Subjects must lie quietly for \geq 5 minutes before supine/semisupine blood pressure and pulse measurements are taken, then assume standing position for 3 minutes before standing blood pressure and pulse measurements are taken. If a subject has orthostatic symptoms upon standing (eg, palpitation, dizziness), they will be assisted and asked to lie down without waiting the 3 minutes for vital sign assessment. Orthostatic measurements may be taken at other vital signs collection timepoints if clinically indicated, at the discretion of the investigator.
- When applicable, vital signs measurements will be obtained before blood draws.

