8.3.1. Time Period and Frequency for Collecting AE and SAE Information

All AEs and SAEs will be collected from the signing of the ICF until completion of study participation (ie, early termination or Follow-up Phone Call) at the timepoints specified in the SoA (Table 1).

Any medical condition that is present at the time that a randomized subject is screened and does not deteriorate (worsen in severity and/or frequency) should be recorded as Medical History and not as an AE. However, if the subject's condition deteriorates at any time during the study, it will be recorded as an AE. AEs characterized as intermittent require documentation of onset and duration of each episode. Pretreatment AEs will be collected and captured in the subject's source documentation from the time the subject signs the ICF until the subject receives study drug. Pretreatment AEs in randomized subjects will additionally be entered on the AE page of the subject's eCRF. Laboratory abnormalities, changes in vital signs, and physical examination findings should be considered AEs and reported on the AE page of the subject's eCRF only if the investigator considers them clinically significant and/or they necessitate intervention.

All SAEs will be recorded and reported to the sponsor or designee immediately and under no circumstance should this exceed 24 hours, as indicated in Appendix 3/Section 10.3. The investigator will submit any updated SAE data to the sponsor within 24 hours of it being available.

Investigators are not obligated to actively seek AEs or SAEs after the conclusion of study participation. However, if the investigator learns of any SAE, including a death, at any time after a subject has been discharged from the study, and he/she considers the event to be reasonably related to the study intervention or study participation, the investigator must promptly notify the sponsor.

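### SAP 7.3 gives two definitions of a positive orthostatic result, and a measured fall without a recorded adverse event enters no planned table

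*SAP*

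**What the plan says.** Three statements in SAP 7.3 bear on this. The first announces a joint assessment: "The change in blood pressure from supine to standing, along with associated adverse events, will be used to assess orthostatic hypotension". The next says that the criteria for a positive test are those in Table 4, and that table holds two blood-pressure thresholds and no AE condition. The text after the table then restricts positives to "Subjects meeting either one of these two criteria and who also have an associated adverse event, as indicated on the eCRF". The planned orthostatic table gives the number and percentage of these subjects by treatment group (or cohort), for baseline and postbaseline.

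The other blood-pressure outputs in the SAP are supine. Section 7.3 plans "Descriptive statistics for body weight and vital signs (ie, oral temperature, supine systolic and diastolic blood pressure, and pulse", with changes from baseline. The blood-pressure and pulse rows of Table 3, on potentially clinically significant values, are supine too. Section 7 adds: "For vital signs, the last supine measurement before dosing will be used as baseline".

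On AE reporting, Protocol 8.3.1 says that vital-sign changes are reported as AEs "only if the investigator considers them clinically significant and/or they necessitate intervention". On purpose, Protocol 2.3.1 says: "Orthostatic vital sign measurements will be taken to evaluate the potential for volume depletion".

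**The concern.** A subject whose systolic pressure falls by 20 mmHg or more on standing, without symptoms, meets Table 4. If the investigator does not judge the change clinically significant and no intervention is needed, there is no AE and the subject is not counted. A reader who sees 0/6 in a dose group cannot tell whether nobody had a fall or whether falls occurred and none was recorded as an AE.

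This matters because the protocol names diarrhea with secondary dehydration as a potential risk and schedules the orthostatic readings to look for volume depletion. Safety is the primary objective. The AE condition also departs from the SAP's own practice: the laboratory, vital-sign and ECG tables of potentially clinically significant values (SAP 7.2 to 7.4) count numeric threshold crossings and require no AE.

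**Working it through.** The documents state no figure on this point, so there is none to reproduce. The check is mainly textual.

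**1. The two definitions.** Table 4, as introduced: systolic fall of at least 20 mmHg or diastolic fall of at least 10 mmHg. The counting rule after it: either fall and an associated AE. A subject with a fall and no AE is positive under the first and negative under the second.

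**2. Can a fall exist without an AE?** Yes. Protocol 8.3.1 makes the AE depend on clinical significance and/or intervention, not on a blood-pressure threshold.

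**3. Would another planned output show the fall?**
- SAP 7.3 descriptive statistics: supine pressure and change from baseline, so no.
- SAP Table 3: supine pressure, supine pulse and weight, so no.
- Protocol 9.4.5: values and changes from baseline in systolic and diastolic pressure; no postural change is named.
- SAP 7.1 AE tables: an AE is needed, so no.
- Listings: SAP 7.3 says that all data are listed, but that sentence names supine pressure. The standing readings are introduced later, with no listing of their own and no Table 4 flag. That they will be listed is a reasonable inference, not an explicit statement.

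**4. Scheduled orthostatic tests per subject.** Protocol 8.2.2 gives "Day 1 predose and 1- and 6-hours postdose, Day 2 predose, Day 7 predose and 1- and 6-hours postdose", plus Day 8 at 24 hours after the Day 7 dose. That is 3 + 1 + 3 + 1 = 8, of which 1 (Day 1 predose) is baseline and 7 are postbaseline.

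**5. Illustration on assumed rates.** Let p be the share of subjects with a postbaseline fall and a the share of those who also have an associated AE. The documents give neither. For a dose group of 6 with independent subjects:
- expected number with a fall but not in the table = 6p(1 − a);
- chance that at least one subject has a fall while the table shows 0/6 = (1 − pa)^6 − (1 − p)^6.

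| p | Expected number missed at a = 1 / 0.5 / 0 | Chance of 0/6 despite a fall, a = 0.5 |
|---|---|---|
| 10% | 0 / 0.3 / 0.6 | 0.735 − 0.531 = 20% |
| 30% | 0 / 0.9 / 1.8 | 0.377 − 0.118 = 26% |
| 50% | 0 / 1.5 / 3.0 | 0.178 − 0.016 = 16% |

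At a = 1 that chance is 0. At a = 0 it is 1 − (1 − p)^6, which is 47%, 88% and 98%.

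**6. Limit on any count of falls.** With an assumed benign fall rate q per test and independent tests, a subject has a baseline fall with probability q and at least one postbaseline fall with probability 1 − (1 − q)^7. For q = 2%, 5% and 10% the postbaseline values are 13%, 30% and 52%, with no drug effect. A count of falls therefore cannot be read against baseline.

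**The case against.** The strongest reply is that requiring both a measurement and a clinical event is a legitimate prespecified choice, applied equally to placebo. Protocol 9.4.5 promises no orthostatic count, so the SAP breaks no commitment. Falls that are clinically significant or need intervention are AEs, and are counted if recorded as associated. With at most 27 subjects and 8 scheduled tests each (27 × 8 = 216 pairs), reading a listing is practicable. Benign falls could also make a count regardless of AE hard to interpret.

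Much of this stands. A reader might infer that the planned count is wrong. It is not wrong under its own rule; it can be low only relative to the Table 4 thresholds. A reader might also infer that volume depletion could go unseen when the dose is raised. The documents do not support that: the Dose Escalation Committee makes blinded reviews of the safety data, "including adverse events (AEs), clinical laboratory test results, vital signs, and 12-lead ECGs", and does not depend on the end-of-study table.

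The reply does not remove the mismatch between the sentence introducing Table 4 and the counting rule, or the absence of any table of measured falls. The listing argument is weakened because neither standing values nor a flag is named. The benign-fall argument governs how a count should be read, and pooled placebo (3 subjects per cohort, so 6 or 9) offers a comparison over the same schedule, though a small one.

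**Conclusion.** The point holds as a minor reporting gap. SAP 7.3 is inconsistent about what counts as positive, and under the rule it applies, a measured Table 4 fall without an AE appears in no planned table. This rests on the text alone.

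The size is unknown and may be zero. The figures above depend wholly on assumed p, a and q and on independence; they show how the rule behaves and are not evidence that falls will be missed. No hypothesis is tested, so no error rate or power is affected. It would also go too far to say that the standing readings are lost: they are collected and will probably be listed, but the SAP should say so.

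**What to change.** Change SAP 7.3 as follows.

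- Tabulate by treatment the number and percentage of subjects who meet either Table 4 criterion at any scheduled postbaseline orthostatic test, regardless of AE. Limit the count to scheduled tests, because Protocol 8.2.2 allows extra ones at the investigator's discretion and the number of tests could then differ between subjects. State that the count is read against pooled placebo, not against the single baseline test.
- Keep the count of subjects with a Table 4 fall and an associated AE as a subset row, and reword the sentences before and after Table 4 so that the two definitions agree.
- Summarise supine-to-standing change in systolic and diastolic pressure by scheduled timepoint and treatment, with the number of paired readings. That number matters because a subject with symptoms on standing lies down without waiting the 3 minutes and may have no standing value.
- State that standing values are listed, with a flag for a Table 4 fall.

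The cost is SAP wording, one extra table row, one by-timepoint table and a listing flag, all from readings already scheduled. The downside is that some benign, asymptomatic falls will be counted in every group, placebo included.
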